## 5.3 Efficacy Endpoints and Analyses

For all efficacy endpoints and analyses, the modified Intent-to-Treat (mITT) population will be used.

### 5.3.1 Primary Endpoint Analysis

The primary efficacy endpoint is the percent change from baseline to Week 6 in LDL-C.

LDL-C value will be measured directly if TG are >400 mg/dL or LDL-C is <50 mg/dL. Baseline is defined as the mean of the values from Week -1 (Visit S2) and predose Day 1/Week 0 (Visit T1). Percent change from baseline is defined as (observed value-baseline)/baseline\*100.

An analysis of covariance (ANCOVA) with treatment group as factor and baseline LDL-C as a covariate will be performed to compare triplet therapy versus placebo for the primary endpoint using the mITT population. The least squares mean (LSM) and standard error (SE) will be provided for both treatment groups, along with the placebo-corrected LSM, its 95% confidence interval (CI), and associated p-value. Statistical testing of primary efficacy endpoint will be 2-sided and conducted at the 5% level of significance. To account for potential unequal variance between the treatment groups, the ANCOVA model will be implemented within mixed model framework and the repeated/group= option will be used to allow estimating the residual variances separately between the groups. Q-Q plot will be performed to assess normality of data by treatment. If the assumptions were severely violated, non-parametric rank based approach will be considered.

An example sas code for ANCOVA analysis is shown as below:

```
class usubjid armcd;
model chg = blres armcd / solution ddfm=kenwardroger;
```

repeated/group=armcd; lsmeans armcd/diff=control ('0') cl;

**PROC MIXED** DATA = adxx;

Missing data for the primary endpoint will be imputed using the last post-baseline observation carried forward (LOCF) procedure (only post-baseline values will be carried forward).

A Secondary analysis for the primary endpoint will be conducted use observed data only.

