4. INTRODUCTION

Bempedoic acid (ETC-1002) is an oral, first-in class, small molecule designed to lower low-density lipoprotein cholesterol (LDL-C). It inhibits adenosine triphosphate-citrate lyase (ACL), an enzyme upstream of 3-hydroxy-3-methylglutaryl coenzyme A (HMG-CoA) reductase in the cholesterol biosynthesis pathway. Bempedoic acid, like both statins and ezetimibe, up-regulates LDL-C receptors. However, unlike statins, bempedoic acid does not inhibit cholesterol synthesis in muscle tissue, therefore it is anticipated that negative muscle-related adverse effects associated with statin use may be avoided by use of bempedoic acid.

Hypercholesterolemic patients have several therapeutic options to lower LDL-C. Statin and nonstatin therapies that lower LDL-C via upregulation of LDL receptors are associated with reduced cardiovascular disease (CVD) risk. Bempedoic acid 180 mg, atorvastatin 20 mg, and ezetimibe 10 mg work by divergent mechanisms to lower LDL-C via up-regulation of LDL receptors. This Phase 2 study in patients with elevated LDL-C is being conducted to characterize the magnitude of LDL-C lowering achievable with this oral triplet therapy.

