7. SELECTION OF PATIENTS

7.1. Subject Inclusion Criteria

Each patient must meet the following criteria to be eligible for this study.

- 1. Provision of written informed consent prior to any study-specific procedure;
- 2. Age ≥18 years or legal age of majority based on regional law, whichever is greater, at Week -6 (Visit S1);
- 3. Fasting calculated LDL-C between 130-189 mg/dL at Week -1 (Visit S2) following washout of all LDL-C-lowering drugs and nutritional supplements;
 - Note: LDL-C may be repeated 1 time with the screening period extended up to 1 week. For those patients who have a repeat LDL-C, the mean of the first value and the repeat value will be used to determine eligibility.
- 4. Patient is sufficiently stable and suitable to undergo washout of all LDL-C-lowering drugs and nutritional supplements for 12 weeks (with potential for 1 week extension) based on Investigator assessment;
- 5. Men and nonpregnant, nonlactating women. Women must be one of the following:
 - a. Naturally postmenopausal defined as ≥ 1 year without menses and:
 - i. \geq 55 years, or
 - ii. <55 years with follicle-stimulating hormone (FSH) ≥40.0 IU/L, or
 - b. Surgically sterile including hysterectomy, bilateral oophorectomy, and/or tubal ligation, or
 - c. Women of childbearing potential willing to use one acceptable method of birth control during the study and for 30 days after the end of treatment including:
 - i. birth control medications,
 - ii. placement of an intrauterine device with or without hormones,
 - iii. barrier methods including condom or occlusive cap with spermicidal foam or spermicidal jelly,
 - iv. vasectomized male partner who is the sole partner for this patient,
 - v. true abstinence (not including periodic abstinence such as calendar, ovulation, symptothermal, postovulation methods, or withdrawal);

There are no protocol-specific birth control requirements for men with partners who are able to become pregnant.

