7.2. Subject Exclusion Criteria

Patients who meet any of the following criteria will not be eligible to participate:

- 1. Body mass index (BMI) >50 kg/m²;
- 2. History of documented clinically significant cardiovascular disease including, but not limited to:
 - a. Myocardial infarction, severe or unstable angina pectoris, coronary angioplasty, coronary artery bypass graft, stroke, transient ischemic attack, cerebrovascular event, symptomatic carotid artery disease, or symptomatic peripheral arterial disease,
 - b. Uncontrolled hypertension, defined as sitting mean systolic blood pressure (SBP) ≥160 mm Hg and/or diastolic blood pressure (DBP) ≥100 mm Hg after sitting quietly for 5 minutes.

Note: At the discretion of the investigator, a single repeat sitting mean SBP and DBP may be completed at a separate visit. For those patients who have repeat sitting mean SBP and DBP assessment, the repeat values will be used to determine eligibility.

- c. An arrhythmia requiring medical intervention,
- d. Abdominal aortic aneurysm,
- e. New York Heart Association (NYHA) Class III and IV heart failure;
- 3. Fasting TG >400 mg/dL at Week -1 (S2);

Note: TG may be repeated 1 time with the screening period extended up to 1 week. For those patients who have a repeat TG, the repeat value will be used to determine eligibility.

- 4. History of type 1 or type 2 diabetes or fasting glucose >125 mg/dL at Week -6 (Visit S1);
- 5. Uncontrolled hypothyroidism, including thyroid-stimulating hormone (TSH) $> 1.5 \times$ the upper limit of normal (ULN) at Week -6 (Visit S1);
- 6. Liver disease or dysfunction, including:
 - a. Positive serology for hepatitis B surface antigen (HBsAg) and/or hepatitis C antibodies (HCV-ABVivi) at Week -1 (Visit S2), or
 - b. Alanine aminotransferase (ALT), aspartate aminotransferase (AST) ≥2 × ULN, and/or total bilirubin (TB) ≥2 × ULN at Week -6 (Visit S1). If TB ≥1.2 × ULN, a reflex indirect (unconjugated) bilirubin will be obtained and if consistent with Gilbert's disease or if the patient has a history of Gilbert's Disease, the patient may be enrolled in the study.

Note: At the discretion of the investigator, a single repeat of ALT, AST, and/or TB may be completed. For those patients who have a repeat ALT, AST, and/or TB, the repeat value will be used to determine eligibility. Also, if test for hepatitis C antibody is positive, but optional reflexive test for hepatitis C ribonucleic acid (RNA) is negative, the patient can be enrolled.

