10.5.3. Treatment Week 0 (Visit T1; Day 1)

Prior to scheduling Visit T1, screening results will be reviewed to determine whether the patient continues to meet eligibility criteria. At Visit T1, a physical exam and urine pregnancy test will also be completed prior to randomization. Patients not meeting all entry criteria at any point prior to randomization will be screen failures.

If the patient has met all inclusion criteria and none of the exclusion criteria, the patient may be randomized into the double-blind Treatment Period.

Patients are considered randomized once all eligibility criteria are confirmed and a randomization number is obtained by the IWRS on the day of first dose.

The patient will undergo the following assessments and procedures at Day 1 (Visit T1):

- Concomitant medication review (ongoing)
- Assess AEs and SAEs
- PE
- Review inclusion/exclusion criteria to establish patient eligibility
- Weight
- Vital signs
- Central clinical laboratory evaluations:
 - Hematology, blood chemistry, and urinalysis
 - Basic fasting lipids (TC, calculated LDL-C, HDL-C, non-HDL-C, and TG)
 - ApoB and hs-CRP
- Urine pregnancy test (in female patients of childbearing potential)
- IWRS contact to obtain the patient randomization number and MED ID number for double-blind IMP
- Dispense double-blind IMP and provide dosing and storage instructions
- Dietary and lifestyle counselling

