10.5.4. Treatment Week 3 (Visit T2; Day 22 ± 3 days)

Patients will undergo the following assessments and procedures at Week 3 (Visit T2):

- Concomitant medication review (ongoing)
- Assess AEs and SAEs
- Weight
- Vital signs
- Central clinical laboratory evaluations:
 - Hematology, blood chemistry, and urinalysis
 - Basic fasting lipids (TC, calculated LDL C, HDL C, non-HDL C, and TG)
- Return of IMP; assessment and recording of IMP dosing adherence
- IWRS contact to obtain new MED ID number for double-blind IMP
- Dispense double-blind IMP and provide dosing and storage instruction
- Dietary and lifestyle counselling

10.5.5. Treatment Week 6 (Visit T3; Day 43 ± 3 days)/End of Study or Early Termination

Patients will undergo the following assessments and procedures at Week 6 and/or End of Study/Early Termination:

- Concomitant medication review (ongoing)
- Assess AEs and SAEs
- PE
- Weight
- Vital signs
- Central clinical laboratory evaluations:
 - Hematology, blood chemistry, and urinalysis
 - Basic fasting lipids (TC, calculated LDL-C, HDL-C, non-HDL-C, and TG)
 - ApoB and hs-CRP
- Return of IMP; assessment and recording of IMP adherence

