11. ASSESSMENT OF EFFICACY

11.3 Assessments of Lipids and hs-CRP

Central clinical laboratory samples will be collected and analyzed for the parameters detailed in Table 3. LDL-C will be calculated or measured directly if TG are >400 mg/dL or LDL-C is <50 mg/dL.

Blood draws for lipids (not safety) must meet the criteria below. If these criteria have not been met, these blood samples will NOT be collected. If these criteria can be met by rescheduling clinic visit to occur within 3 days, these blood samples will be collected at the rescheduled clinic visit only.

- Blood samples will be drawn after a minimum 10-hour fast (water and concomitant medications [but not IMP] is allowed)
- Blood samples will be drawn only if patient ingested IMP the previous day

Patients are to be in a seated position during the blood collection. Collection schedule and instructions are provided in the Central Clinical Laboratory Manual. A description of the sample collection, storage, and shipping as well as monitoring and management of abnormal laboratories are described in Section 12.1.5.

When vital signs and laboratory samples are to be collected at the same time point, vital sign measurements will precede laboratory sample collection.

Table 3: Central Clinical Laboratory Parameters (Lipids and hs-CRP)

| Clinical Laboratory Test | Clinical Laboratory Test |
|--|--|
| Basic Lipid Parameters | Other Parameters |
| Total cholesterol (TC) | High-sensitivity C-reactive protein (hs-CRP) |
| Calculated low-density lipoprotein cholesterol (LDL-C) and non-HDL-C | Apolipoprotein B (ApoB) |
| High-density lipoprotein cholesterol (HDL-C) | |
| • Triglycerides (TG) | |

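### Does measuring LDL-C directly below 50 mg/dL, which will happen almost only on triplet therapy, undermine the estimated LDL-C lowering?

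*SAP*

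**What the plan says.** SAP 5.3.1 places the measurement rule with the primary endpoint: "LDL-C value will be measured directly if TG are >400 mg/dL or LDL-C is <50 mg/dL". Protocol 11.3 has the same two triggers: "LDL-C will be calculated or measured directly if TG are >400 mg/dL or LDL-C is <50 mg/dL".

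Baseline LDL-C is the mean of the Visit S2 and predose Visit T1 values (SAP 5.2.2). Inclusion criterion 3 (Protocol 7.1) requires a calculated value of 130 to 189 mg/dL at S2. Exclusion criterion 3 (Protocol 7.2) removes patients with triglycerides above 400 mg/dL at S2. The T1 panel in Protocol 10.5.3 is "Basic fasting lipids (TC, calculated LDL-C, HDL-C, non-HDL-C, and TG"), so calculation is the default there too.

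The primary analysis is an ANCOVA of percent change at Week 6 with LOCF and separate residual variances by arm. A rank-based approach is to be considered if assumptions are severely violated. SAP 5.3.1 adds: "A Secondary analysis for the primary endpoint will be conducted use observed data only". SAP 5.3.2 applies a similar ANCOVA to non-HDL-C, TC and ApoB among other markers, and plans a listing of lipid data from all visits.

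**The concern.** The numerator and denominator of the percent change can come from different methods, and whether they do depends on the outcome. A triplet patient who responds strongly has a calculated baseline and a direct Week 6 value, while a placebo patient almost never does. If direct and calculated LDL-C differed systematically below 50 mg/dL, the difference would enter the triplet mean, stay out of the placebo mean, and pass into the placebo-corrected estimate. The confidence interval would not reflect it.

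Protocol 4 says the study is run "to characterize the magnitude of LDL-C lowering achievable with this oral triplet therapy", so the size of the effect matters as well as the test. None of the planned analyses of the primary endpoint uses one method throughout, and no table counts the directly measured values.

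**Working it through.** **Inputs from the documents.** Direct measurement below 50 mg/dL; S2 LDL-C 130 to 189 mg/dL; about 60 patients randomized 2:1, hence about 40 and 20.

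**Inputs not in the documents.** The public text gives no expected effect, SD or between-method gap, so there is no planned figure to reproduce. Assumed here: baseline normal with mean 155 and SD 15, truncated to 130-189 (resulting mean 156.1); mean triplet change -45% to -65%; SD of percent change 10 to 15 points; a constant gap of 5 or 10 mg/dL on every value below 50.

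**Step 1: fall needed to trigger the rule.** 1 - 50/baseline:
- at 130: 1 - 50/130 = 61.5%
- at 189: 1 - 50/189 = 73.5%

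These bounds are not strict, because T1 has no range limit. For example, S2 of 132 and T1 of 112 give a baseline of (132 + 112)/2 = 122 and a needed fall of 1 - 50/122 = 59%.

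**Step 2: how many patients switch, and what a gap would do.** The shift in the triplet mean is roughly share × gap / mean baseline × 100. For a share of 0.429 and a gap of 5 mg/dL this is 0.429 × 5/156.1 × 100 = 1.37 points. Simulation gives 1.40, because switchers have slightly lower baselines. Simulated ranges over SD 10 to 15:

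| Mean triplet change | Share below 50 mg/dL | Patients of 40 | Shift, 5 mg/dL gap (points) |
|---|---|---|---|
| -45% | 1.4-6.8% | 0.6-2.7 | 0.05-0.22 |
| -50% | 4-12% | 1.7-4.9 | 0.15-0.40 |
| -55% | 11-20% | 4.4-8.1 | 0.36-0.66 |
| -60% | 23-31% | 9.1-12.2 | 0.75-1.00 |
| -65% | 40-43% | 15.8-17.2 | 1.30-1.40 |

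A 10 mg/dL gap doubles the last column, to at most 2.80 points. On placebo (mean change 0 or -5%) the share is at most 0.002%, or about 0.1% if the SD is 20. The switch is therefore confined to triplet in practice.

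**Step 3: compare with the precision of the estimate.** SE of the difference = SD × √(1/40 + 1/20):
- SD 10: 2.74
- SD 13: 3.56
- SD 15: 4.11

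The worst ratio is at -65%, SD 10 and a 10 mg/dL gap: 2.60/2.74 = 0.95 SE. With a slightly wider baseline (SD 16, values clipped to the range) it is 2.70/2.74 = 0.99 SE. To reach one full SE, the methods would have to differ by more than 10 mg/dL, a fifth of the 50 mg/dL threshold, in the same direction for every low value.

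**Step 4: the primary test.** Taking no change on placebo, the effect is 45/4.11 = 11 SE at the weak end and 65/2.74 = 23.7 SE at the strong end. A shift below one SE cannot change the conclusion.

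**Step 5: the responder endpoints.** With a baseline of at least 130, half of baseline is at least 65. A value below 50 would need a gap of more than 65 - 50 = 15 mg/dL to lose the 50% response, and more than 70 - 50 = 20 mg/dL to lose the below-70 status. Even at the baseline of 122 in Step 1, the first margin is 61 - 50 = 11 mg/dL. Gaps of 5 or 10 mg/dL change neither endpoint.

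**Step 6: what the existing plan already offers.** Non-HDL-C, TC and ApoB do not depend on how LDL-C is obtained, and they are analyzed in a similar way. The lipid listing contains LDL-C and triglycerides at each visit. Because the trigger is a fixed rule on those values, the number of direct measurements can be closely approximated from it.

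**The case for a change.** The strongest case for the concern is that its factual premises are correct. Baseline and low post-baseline values do come from different methods, the switch does follow the outcome, and any offset would fall on one arm and lie outside the confidence interval. The observed-data analysis addresses missing data, not method. Non-HDL-C and ApoB are different analytes and cannot show what the switch does to the LDL-C estimate. TC, HDL-C and triglycerides are collected at every lipid visit, so a calculated value could be derived for a sensitivity analysis at little cost, and a count by arm would tell the reader at once whether the issue is trivial.

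All of that stands, but it does not establish an error. An unequal frequency of direct measurement biases the estimate only if the two methods disagree in that range, and the documents report neither the size nor the direction of any disagreement. Zero is as compatible with the text as 5 or 10 mg/dL.

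The proposed sensitivity analysis would not settle the matter either. It would replace direct values with calculated ones at low levels, where calculation may be the less exact method. If the two results differed, the analysis could not say which one was off. The documents also do not name the formula to be used. The missing count and method flag are real gaps in reporting, but filling them would leave the planned primary analysis and its result unchanged.

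**Conclusion.** The concern does not hold. The measurement rule is fixed in advance, agrees between the protocol and the SAP, and applies to both arms on laboratory criteria. Followed as written, it gives a sound estimate of LDL-C lowering. The asymmetry between arms is real, but it reflects the treatment effect and is not bias unless the methods disagree, which nothing in the documents shows.

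Under assumed gaps of 5 to 10 mg/dL and mean triplet changes of -45% to -65% with an SD of 10 to 15 points, the estimate would move by 0.05 to 2.8 points. That is always less than one standard error, and it has no consequence for the primary test or the responder endpoints. The gap, effect and SD are all assumptions, since the public text gives none of them. A constant gap well above 10 mg/dL would change the assessment of size, but there is no basis in the documents for supposing one. A table of directly measured values by arm and visit would be useful in the study report as a matter of preference; the plan does not need to be changed.

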### 5.3.2 Secondary Efficacy Endpoint Analyses

Secondary endpoints based on percent change from baseline to Week 6 in additional lipid and cardiometabolic biomarkers, will be analyzed in a similar manner as the primary efficacy endpoint. Baseline for non-HDL-C, HDL-C, TC, and TG is defined as the mean of the values from Week -1 (Visit S2) and predose Day 1/Week 0 (Visit T1), while baseline for ApoB and hs-CRP is defined as the predose Day 1/Week 0 (Visit T1) value.

Confidential Page 12 of 18

An analysis of covariance (ANCOVA) with treatment group as factor and baseline as a covariate will be performed to compare triplet therapy versus placebo for the secondary endpoints using the mITT population. Missing values at Week 6 will be imputed using the last observation carried forward (LOCF) procedure (only post-baseline values will be carried forward). The least squares mean (LSM) and standard error (SE) will be provided for both treatment groups, along with the placebo-corrected LSM, its 95% confidence interval (CI), and associated p-value. Q-Q plot will be performed to assess normality of data by treatment. If the assumptions were severely violated, non-parametric rank based approach will be considered.

Statistical testing of secondary efficacy endpoints will be 2-sided and conducted at the 5% level of significance with no adjustment for multiple comparisons, and all p-values will be considered descriptive only.

Analyses using observed data only for the secondary efficacy endpoints will also be performed.

Percent of patients with LDL-C <70 mg/dL at Week 6 and LDL-C reduction ≥50% from baseline at Week 6 will be summarized by treatment group. Comparisons between treatment groups will be performed using Fisher's exact test or Pearson's chi-square test on observed data and LOCF data.

Lipid and cardiometabolic data from all visits will be listed.

# 5.4 Safety Endpoints and Analyses

For all safety endpoints, the safety population (SP) will be used. Descriptive summary will be provided for safety endpoints.

The summarization of AEs will include only TEAEs (defined as AEs that begin or worsen after the first dose of double-blind IMP until 30 days after last dose of IMP). All TEAEs, SAEs, AEs leading to withdrawal of IMP, fatal AEs and AEs of special interest will be summarized by MedDRA SOC and preferred term in descending order of frequency by treatment group.

Clinical safety laboratories, including hematology, blood chemistry, glucose, and urinalysis; PE findings; vital signs; and weight will be summarized by the value and by change or percent change from baseline in the value (where appropriate) at each postbaseline time point.

### 5.4.1 Adverse Events (AEs)

AEs will be coded using the Medical Dictionary for Regulatory Activities (MedDRA) Version 19.1 or later and will be categorized by system organ class (SOC) and preferred term (PT). Patients with AEs that are ongoing at study completion or study withdrawal must be followed until resolution, until determined to be stable/chronic, or for 30 days after the last study visit, whichever comes first. Summary tables will focus on TEAEs; however, listings will include all AEs (with non-TEAEs flagged).

Confidential Page 13 of 18

In summary tables, TEAEs will be counted as "Not Related" if relationship to study drug was recorded as 'Not Related' or "Unlikely". Events will be counted as "Related" if relationship to study drug was recorded as 'Possible', 'Probable', 'Definite' or if relationship to study drug is missing.

The severity of the AE will be characterized as mild, moderate, or severe, to the following definitions:

- Mild: Events are usually transient and do not interfere with the patient's daily activities
- Moderate: Events introduce a low level of inconvenience or concern to the patient and may interfere with daily activities
- Severe: Events interrupt the patient's usual daily activity, are incapacitating with inability to do usual activities, or significantly affect clinical status and warrant intervention and/or close follow-up

Overviews of TEAEs will be presented by treatment group containing the following counts and percentages for:

- patients with TEAEs
- patients with TEAEs by SOC and PT
- patients with TEAEs by maximum severity
- patients with treatment-related TEAEs
- patients with treatment-emergent serious adverse events (TE SAEs)
- patients with TE SAEs by SOC and PT
- patients with TE SAEs by maximum severity
- patients with treatment-related TE SAEs
- withdrawal from study drug due to TEAEs

AE summaries will include cumulative incidence (percent of patients experiencing the AE). If appropriate, absolute and relative risk differences will be calculated using both cumulative incidence and incidence rates.

The AE overview summaries will count a patient at most once in each AE category (at the "highest/most extreme" designation of each category regardless of preferred term) and percentages will be based on the total number of patients in the safety population.

In addition to a comprehensive listing of all AEs (with non-TEAEs flagged), separate listings will be generated for SAEs, AEs resulting in withdrawal of study drug, and AEs with a fatal outcome.

